7.1. Adverse Events Analyses

Adverse events analyses including the analysis of adverse events (AEs) and Serious (SAEs) will be based on GSK Core Data Standards. The details of the planned displays are provided in [Appendix 10: List of Data Displays](#).

Adverse Events

A listing of AE records for all participants who reported AEs will be produced.

7.2. Clinical Laboratory Analyses

Laboratory evaluations including the analyses of chemistry laboratory tests, hematology laboratory tests, and liver function tests will be based on GSK Core Data Standards. The details of the planned displays are in [Appendix 10: List of Data Displays](#) and include the following tests:

Laboratory Assessments	Parameters		
Hematology	Platelet count	RBC indices:	WBC count with Differential
	RBC count	MCV	Neutrophils
	Reticulocyte count	MCH	Lymphocytes
	Hgb	MCHC	Monocytes
	Hematocrit	RDW	Eosinophils
	WBC count (Absolute)		Basophils
Clinical Chemistry ¹	Sodium (serum)	AST ¹	Carbon Dioxide (total)
	Potassium (serum)	ALT ¹	Albumin
	Creatinine (serum)	Chloride (serum)	Urea (serum)
	Glucose	Bilirubin (total and direct/indirect)	Alkaline Phosphatase
Other laboratory tests	Serum ferritin	TSAT	hs-CRP
	Total cholesterol	LDL-C (direct)	HDL-C
	Triglycerides	Serum/Urine hCG pregnancy test ²	FSH ³
	HbA1c	Folate	Vitamin B ₁₂
	Serology (hepatitis B surface antigen [HBsAg], and hepatitis C virus antibody)		

7.3. Other Safety Analyses

The analyses of non-laboratory safety test results including ECGs and vital signs will be based on GSK Core Data Standards, unless otherwise specified. The details of the planned displays are presented in [Appendix 10: List of Data Displays](#).

8. PHARMACODYNAMIC ANALYSES

8.1. Primary Pharmacodynamic Analyses

8.1.1. Endpoint / Variables

The endpoint of interest is FBF ratio.

FBF ratio is calculated as the FBF of the subject's treatment arm divided by the subject's non-treatment arm. The treatment arm is given either saline or the challenge agent. The non-treatment arm is given nothing.

CONFIDENTIAL

205767

The FBF measurement is calculated from the average of 5 values as recorded on the LabChart file. The 5 values of FBF are recorded manually from a blinded central reader reviewing the subject's FBF LabChart file.

8.1.2. Summary Measure

The summary measure of interest is the change in FBF ratio from Day 1 to Day 42 in response to acetylcholine.

If FBF procedure is repeated for Day 1 and/or Day 42, this data will take the place of the original Day 1 and Day 42 data respectively. A quality control (QC) check will be performed on the FBF data before the final analyses. The QC check will be to assess negative and extreme values for FBF (**FBF**).

Descriptive statistics (n, arithmetic mean, standard deviation (SD), minimum, median, maximum) will be calculated by treatment group for change in FBF ratio endpoints.

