2. SUMMARY OF KEY PROTOCOL INFORMATION

2.1. Changes to the Protocol Defined Statistical Analysis Plan

Changes from the originally planned statistical analysis specified in the protocol are outlined in [Table 1](#).

Table 1 Changes to Protocol Defined Analysis Plan

Protocol	Reporting & Analysis Plan	
Statistical Analysis Plan	Statistical Analysis Plan	Rationale for Changes
• 10.1.2 Sample Size Re-estimation	• Sample size re-estimation will not be performed	• The study was terminated
• 10.3.3 Other Analyses (Pharmacodynamic)	• No statistical analyses will be performed; only summary statistics will be reported. We will not perform exploratory analyses and sensitivity analysis.	• Since the study was terminated and we have only 4 completed subjects to report. Therefore, statistical analysis will not be performed.

CONFIDENTIAL

205767

Protocol	Reporting & Analysis Plan	
Statistical Analysis Plan	Statistical Analysis Plan	Rationale for Changes

 10.3.4 Interim Analyses Enrolled population is not defined in the protocol 	
 Interim analyses will not be performed Enrolled population added in the RAP with the below definition. "All Randomized Participants" 	
 The study was terminated This population is required for data disclosure displays

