2.4. Statistical Hypotheses

The primary endpoint is to compare the effect of daprodustat to darbepoetin alfa on change in FBF ratio from Day 1 to Day 42 in response to acetylcholine. The estimand of interest is the effect of 6 weeks of randomized treatment on the primary endpoint.

Null: The difference between daprodustat and darbepoetin alfa on the acetylcholine-induced change (from Day 1) in FBF ratio at Day 42 is 0.

Alternative: The difference between daprodustat and darbepoetin alfa on the acetylcholine-induced change (from Day 1) in FBF ratio at Day 42 is not 0.

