10.6.4. Pharmacodynamic

Primary/Principle Secondary/Secondary/Exploratory Endpoints
FBF Ratio/Absolute FBF

 • If either a Day 1 Repeat or Day 42 Repeat measurement is available for forearm blood flow, the repeat value will be used instead. • Forearm blood flow for a given challenge agent dose (infused arm), or for values from the non-infused arm, will be the mean of 5 continuous time point values. • Forearm blood flow ratio is defined as the ratio of a subject's treatment (infused) arm value divided by the non-treatment (non-infused) arm value 
 ○ First, the mean of both the infused and non-infused arm will be taken separately for the given five measurements before going into the ratio calculation. An example of this is shown in the table below:

CONFIDENTIAL

205767

Primary/Principle Secondary/Secondary/Exploratory Endpoints			
	Infused	Non-Infused	
Measurement 1	1.2	1.01	
Measurement 2	1.1	1	
Measurement 3	1.4	1.2	
Measurement 4	1.5	1.1	
Measurement 5	1.6	1.3	FBF Ratio
Average	1.36	1.122	1.212121212

- Absolute forearm blood flow is defined as the infused arm value.

Secondary Endpoint
PWV Dataset
For the PWV dataset, there are two recorded values for each variable per day, with the option to collect a third value if the first two values varied (Refer: SRM) too much from each other. The average of the two closest absolute values will be used for analysis purposes.

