10.10.6. Pharmacodynamic Tables

Pharmacodynamic: Tables					
No.	Population	IDSL / Example Shell	Title	Programming Notes	Deliverable [Priority]
Primary Endpoint					
3.1.	PDPP	PD_T1	Summary of Forearm Blood Flow Ratio in Response to Acetylcholine		SAC
3.2.	PDPP	PD_T2	Summary of Change in Forearm Blood Flow Ratio (Day 1 to Day 42), Acetylcholine		SAC
Principle Secondary Endpoint					
3.3.	PDPP	PD_T3	Summary of Change in Absolute Forearm Blood Flow (Day 1 to Day 42), Acetylcholine		SAC

CONFIDENTIAL

205767

Pharmacodynamic: Tables					
No.	Population	IDSL / Example Shell	Title	Programming Notes	Deliverable [Priority]
Secondary Endpoints					
3.4.	PDPP	PD_T2	Summary of Change in Forearm Blood Flow Ratio (Day 1 to Day 42), Sodium Nitroprusside		SAC
3.5.	PDPP	PD_T3	Summary of Change in Absolute Forearm Blood Flow (Day 1 to Day 42), Sodium Nitroprusside		SAC
3.6.	PDPP	PD_T2	Summary of Change in Forearm Blood Flow Ratio (Day 1 to Day 42), L-NMMA		SAC
3.7.	PDPP	PD_T3	Summary of Change in Absolute Forearm Blood Flow (Day 1 to Day 42), L-NMMA		SAC
3.8.	PDPP	PD_T4	Summary of Augmentation Index and Pulse Wave Velocity		SAC
3.9.	PDPP	PD_T5	Summary of Change in Augmentation Index (Day 1 to Day 42)		SAC
3.10.	PDPP	PD_T5	Summary of Change in Pulse Wave Velocity (Day 1 to Day 42)		SAC

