10.11. Appendix 11: Example Mock Shells for Data Displays

CONFIDENTIAL

205767

Example: SAFE1

Protocol: 205767

Population: Safety

Page 1 of n

Table 2.1
Summary of Lab Values

Parameter	Treatment	N	Visit	n	Mean	SD	Min	P25	Median	P75	Max
HGB (g/dL)	Dapro	xxxx	Screening [1]	Xxxxx	xx.x	xx.xx	Xx	xx.x	xx.x	xx.x	Xx
			Day 1	Xxxxx	xx.x	xx.xx	Xx	xx.x	xx.x	xx.x	Xx
			Repeat Day 1	Xxxxx	xx.x	xx.xx	Xx	xx.x	xx.x	xx.x	Xx
			Day 14	Xxxxx	xx.x	xx.xx	Xx	xx.x	xx.x	xx.x	Xx
			Day 28	Xxxxx	xx.x	xx.xx	Xx	xx.x	xx.x	xx.x	Xx
			Day 42	Xxxxx	xx.x	xx.xx	Xx	xx.x	xx.x	xx.x	Xx
			Repeat Day 42	Xxxxx	xx.x	xx.xx	Xx	xx.x	xx.x	xx.x	Xx
			Follow-up	Xxxxx	xx.x	xx.xx	Xx	xx.x	xx.x	xx.x	Xx
rhEPO		xxxx	Screening [1]	Xxxxx	xx.x	xx.xx	Xx	xx.x	xx.x	xx.x	Xx
			Day 1	Xxxxx	xx.x	xx.xx	Xx	xx.x	xx.x	xx.x	Xx
			Repeat Day 1	Xxxxx	xx.x	xx.xx	Xx	xx.x	xx.x	xx.x	Xx
			Day 14	Xxxxx	xx.x	xx.xx	Xx	xx.x	xx.x	xx.x	Xx
			Day 28	Xxxxx	xx.x	xx.xx	Xx	xx.x	xx.x	xx.x	Xx
			Day 42	Xxxxx	xx.x	xx.xx	Xx	xx.x	xx.x	xx.x	Xx
			Repeat Day 42	Xxxxx	xx.x	xx.xx	Xx	xx.x	xx.x	xx.x	Xx
			Follow-up	Xxxxx	xx.x	xx.xx	Xx	xx.x	xx.x	xx.x	Xx

[1] Screening is an average of all screening values.

CONFIDENTIAL

205767

Example: PD_T1
 Protocol: 205767
 Population: PDPP

Page 1 of n

Table 3.1
 Summary of Forearm Blood Flow Ratio in Response to Acetylcholine

Treatment: Daprodustat	Challenge Agent	FBF Control Arm		FBF Infused Arm		Ratio [1]
		Day 1	Day 42	Day 1	Day 42	
Saline	n	3	3	3	3	3
	Mean	1.75	1.75	1.75	1.75	1.75
	SD	0.834	0.834	0.834	0.834	0.834
	Median	1.65	1.65	1.65	1.65	1.65
	Min.	1.0	1.0	1.0	1.0	1.0
	Max	1.4	1.4	1.4	1.4	1.4
7.5 ug	n	3	3	3	3	3
	Mean	1.75	1.75	1.75	1.75	1.75
	SD	0.834	0.834	0.834	0.834	0.834
	Median	1.65	1.65	1.65	1.65	1.65
	Min.	1.0	1.0	1.0	1.0	1.0
	Max	1.4	1.4	1.4	1.4	1.4
15 ug	n	3	3	3	3	3
	Mean	1.75	1.75	1.75	1.75	1.75
	SD	0.834	0.834	0.834	0.834	0.834
	Median	1.65	1.65	1.65	1.65	1.65
	Min.	1.0	1.0	1.0	1.0	1.0
	Max	1.4	1.4	1.4	1.4	1.4

[1] The Day 42 ratio is calculated by taking the subject's Day 42 treatment (infused) arm and dividing by the Day 42 non-treatment (control) arm value. The Day 1 ratio is calculated by taking the subject's Day 1 treatment (infused) arm and dividing by the Day 1 non-treatment (control) arm value. The overall ratio is determined by taking the subject's Day 42 ratio and dividing by the Day 1 ratio.

CONFIDENTIAL

205767

Example: PD_T2
 Protocol: 205767
 Population: PDPP

Page 1 of n

Table 3.2
 Summary of Change in Forearm Blood Flow (FBF) Ratio (Day 1 to Day 42), Acetylcholine

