
Challenge Agent	Daprodustat FBF Ratio [1]	rhEPO FBF Ratio [1]	Change in FBF Ratio [2]
Saline	n Mean SD Median Min. Max	3 1.75 0.834 1.65 1.0 1.4	3 1.75 0.834 1.65 1.0 1.4
7.5 ug	n Mean SD Median Min. Max	3 1.75 0.834 1.65 1.0 1.4	3 1.75 0.834 1.65 1.0 1.4
15 ug	n Mean SD Median Min. Max	3 1.75 0.834 1.65 1.0 1.4	3 1.75 0.834 1.65 1.0 1.4

[1] The Day 42 ratio is calculated by taking the subject's Day 42 treatment (infused) arm and dividing by the Day 42 non-treatment (control) arm value. The Day 1 ratio is calculated by taking the subject's Day 1 treatment (infused) arm and dividing by the Day 1 non-treatment (control) arm value. The overall ratio is determined by taking the subject's Day 42 ratio and dividing by the Day 1 ratio.

CONFIDENTIAL

205767

[2] The FBF ratio difference between Daprodustat and rhEPO.

CONFIDENTIAL

205767

Example: PD_T3

Protocol: 205767

Population: PDPP

Page 1 of n

Table 3.3
Summary of Change in Absolute FBF (Day 1 to Day 42), Acetylcholine

Treatment	Challenge Agent	N	Visit	n	Mean	SD	Median	Min.	Max.
Dapro	Saline	4	AVG. Day 1			4	1.06	6.695	1.50
			AVG. Day 42			4	-0.17	5.722	0.17
	7.5 ug	4	AVG. Day 1			4	1.06	6.695	0.7
			AVG. Day 42			4	-0.17	5.722	-0.6
	15 ug	4	AVG. Day 1			4	1.06	6.695	1.7
			AVG. Day 42			4	-0.17	5.722	0.5
	30 ug	4	AVG. Day 1			4	1.06	6.695	0.7
			AVG. Day 42			4	-0.17	5.722	-0.6
rhEPO	Saline	4	AVG. Day 1			4	1.06	6.695	0.7
			AVG. Day 42			4	-0.17	5.722	-0.6
	7.5 ug	4	AVG. Day 1			4	1.06	6.695	1.7
			AVG. Day 42			4	-0.17	5.722	0.5
	15 ug	4	AVG. Day 1			4	1.06	6.695	0.7
			AVG. Day 42			4	-0.17	5.722	-0.6
	30 ug	4	AVG. Day 1			4	1.06	6.695	1.7
			AVG. Day 42			4	-0.17	5.722	0.5

CONFIDENTIAL

205767

Example: PD_T4
 Protocol: 205767
 Population: PDPP

Page 1 of n

Table 3.8
 Summary of Augmentation Index and Pulse Wave Velocity

Treatment		n	Day 1	Day 42
Dapro	Augmentation Index	n	3	3
		Mean	25.0	25.0
		SD	0.15	0.15
		Median	25.5	25.5
		Min.	20	20
	Pulse Wave Velocity	Max	30	30
		n	3	3
		Mean	7.75	7.75
		SD	0.834	0.834
		Median	6.65	6.65
rhEPO	Augmentation Index	Min.	7.0	7.0
		Max	9.5	9.5
		n	1	1
		Mean	25.0	25.0
		SD	0.15	0.15
	Pulse Wave Velocity	Median	25.5	25.5
		Min.	20	20
		Max	30	30
		n	1	1
		Mean	25.0	25.0

Example: PD_T5
 Protocol: 205767

Page 1 of n

CONFIDENTIAL

205767

Population: PDPP

Table 3.9
Summary of Change in Augmentation Index and Pulse Wave Velocity (Day 1 to Day 42)

Treatment		N	Visit						
				n	Mean	SD	Median	Min.	Max.

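### Does the SAP need to name a primary acetylcholine dose, or a pooled contrast, for the change in FBF ratio?

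*SAP*

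**What the plan says.** SAP 8.1.2 states the primary quantity in the singular: "The summary measure of interest is the change in FBF ratio from Day 1 to Day 42 in response to acetylcholine". A little further on, the same section says that descriptive statistics "will be calculated by treatment group for change in FBF ratio endpoints", in the plural. SAP 2.4 carries a single null hypothesis: "The difference between daprodustat and darbepoetin alfa on the acetylcholine-induced change (from Day 1) in FBF ratio at Day 42 is 0". None of these statements names an acetylcholine dose or a rule for combining doses.

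Protocol 7.1.2.1 infuses acetylcholine at 7.5, 15 and 30 µg/min, and SAP 10.6.4 derives forearm blood flow separately for each dose. SAP 10.10.6 lists Table 3.2 under the primary endpoint as "Summary of Change in Forearm Blood Flow Ratio (Day 1 to Day 42), Acetylcholine". Its shell in Appendix 11 has one block per level. Footnote 1 builds each participant's figure by taking the "Day 42 ratio and dividing by the Day 1 ratio", and footnote 2 describes a further column as "The FBF ratio difference between Daprodustat and rhEPO".

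Protocol 10.3.3 had asked for one daprodustat/darbepoetin ratio from a model with dose and treatment-by-dose terms. SAP 2.1 withdraws that analysis after termination, with 4 completed subjects: "No statistical analyses will be performed; only summary statistics will be reported".

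**The concern.** One primary measure is named and one hypothesis is stated, yet the primary table produces a between-arm comparison at each level. If the three doses disagree, a writer could lead with whichever looks best after seeing the values.

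The shell adds to the doubt in three ways:

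- A between-arm difference makes sense for a mean or a median but not for an SD, minimum or maximum, and footnote 2 does not say which statistic is meant.
- The protocol's estimate was a ratio between arms, while footnote 2 speaks of a difference.
- The FBF-ratio shells (Tables 3.1 and 3.2) print saline, 7.5 and 15 µg, while the absolute-FBF shell (Table 3.3) also prints 30 µg.

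Were a test still planned, this would matter a good deal, because the size and power of the study are calculated for one contrast that the documents never tie to a dose or an average.

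**Working it through.** **The plan's own figure.** Protocol 10.1 gives 80% power with 25 per arm, CV 0.277, a 25% difference and alpha 5%; the table in 10.1.1 gives 81%. On the log scale:

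- SD = sqrt(ln(1 + 0.277²)) = 0.2719, which matches the 0.272 in Protocol 10.3.4.
- Effect = ln(1.25) = 0.2231.
- Noncentrality = 0.2231 / (0.2719 × sqrt(2/25)) = 2.90 on 48 degrees of freedom, so power is 81.1%.

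The figure reproduces, and it is for a single contrast with no dose dimension. The missing definition therefore goes back to the protocol.

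**What following the SAP literally would produce.**

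| Element | Where | Result |
|---|---|---|
| Flow and ratio | SAP 10.6.4 | one value per participant per level |
| Summary | SAP 8.1.2, 8.1.5 | descriptive statistics by arm |
| Display | Table 3.2 shell | one block per level, no pooled row, none marked primary |
| Test or interval | SAP 2.1 | none |

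A sentence saying that all doses are reported together, that none is primary and that nothing is pooled would describe this same output. It would alter no number.

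**How far the doses could diverge by chance.** Assumptions, since the documents do not give these: log SD 0.2719 at each dose, no true effect, 4 completers split 2:2 or 3:1, and within-participant correlation rho between doses.

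Expected range of the three per-dose contrasts on the log scale = 1.693 × 0.2719 × sqrt((1 − rho)(1/n1 + 1/n2)). Chance that they do not all share a sign = 3/4 − 3·arcsin(rho)/(2π).

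| rho | Range, 2:2 | Range, 3:1 | Signs differ |
|---|---|---|---|
| 0.3 | 0.39 | 0.44 | 60% |
| 0.5 | 0.33 | 0.38 | 50% |
| 0.9 | 0.15 | 0.17 | 22% |

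Simulation on the Day 42/Day 1 ratio scale used in the shell gives 0.41–0.47, 0.34–0.39 and 0.16–0.18, with the same sign results.

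**Would naming one figure help?** With a 2:2 split, the standard error of a single-dose contrast is 0.2719 × sqrt(1/2 + 1/2) = 0.27. For the average of three doses, multiply by sqrt((1 + 2·rho)/3), which gives 0.20, 0.22 and 0.26 for rho 0.3, 0.5 and 0.9. The planned effect is 0.22. Either choice is about as noisy as the effect it would describe.

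**The shell.** In the public text the Table 3.2 header has three data columns, but each level shows only two blocks of values. The printed example therefore cannot settle what the difference column holds, or whether the missing 30 µg row is more than a page cut. Protocol 9.6.1.2 treats all three acetylcholine infusions as the complete procedure, so a programmer would include all three.

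**The case for a change.** The strongest case for a change is that a treatment comparison survives the withdrawal of inference, sits under the primary endpoint, and is defined only by a loose footnote. Saying now that no dose is primary would cost a sentence and would remove any room for choosing a headline later. SAP 2.4, read alone, also looks as if a test is still intended.

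Part of this stands. SAP 8.1.2 does not list the doses, and footnote 2 leaves the statistic and the scale to the programmer.

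The rest carries less weight:

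- SAP 2.4 belongs to Section 2, which summarises protocol information, and SAP 2.1 in that same section rules out any statistical analysis.
- The change of scale is slight. Protocol Section 10 and SAP 2.4 both already word the hypothesis as a difference, and the ratio came from back-transforming a model that will not be run.
- Each arm's own summary is listed beside the difference column, so a reader can form either a difference or a ratio.
- Selective emphasis would be visible at once: every level is tabulated, and Listing 17 shows each participant's flow by agent dose.
- The undefined contrast in Protocol 10.3.3 is real but belongs to a withdrawn analysis.

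**Conclusion.** No change follows. The SAP is silent on a primary acetylcholine dose, but its derivations and displays already report every level descriptively with none singled out, and no test or interval depends on the choice. What is missing is a dose list and a fuller footnote, which analysts can supply without affecting a result. The chance spread between doses is large (0.15 to 0.44 on the log scale under the assumed SD, splits and correlations), but it measures how little 4 completers can show and would be the same with a dose named. The conclusion rests on the report keeping to summary statistics with all levels shown. If the protocol's model or any test were brought back, the contrast across doses would first have to be defined.

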The other secondary endpoint evaluating vascular compliance will make use of two models. The first model for augmentation index will utilize an ANCOVA model with terms for treatment group (daprodustat/darbepoetin alfa), challenge agent dose, treatment*challenge agent dose interaction term, augmentation index on Day 1, gender, and site. The second model for pulse wave velocity will utilize an ANCOVA model with terms for the treatment group (daprodustat/darbepoetin alfa), challenge agent dose, treatment*challenge agent dose interaction term, PWV on Day 1, gender, and site.

The exploratory endpoint looking at the relationship between diabetes status and endothelial function will use a similar ANCOVA model as our primary endpoint, adding in the indicator variable diabetes. This will be explored for all three challenge agents and modeled for FBF ratio and absolute FBF.

The last exploratory endpoint will analyze the FBF dose response relationships for each of the three challenge agents.

Sensitivity analyses will be performed for all endpoints analysing FBF ratio. Instead of FBF ratio, percent change from saline infusion and absolute change from saline infusion will be modelled.

Distributional assumptions underlying the statistical analyses will be assessed by visual inspection of the residual plots. Normality will be examined by normal probability plots, while homogeneity of variance will be assessed by plotting the residuals against the predicted values for the model.

Descriptive statistics (n, arithmetic mean and corresponding 95% confidence interval, standard deviation (SD), minimum, median, maximum) will be calculated by treatment group for all PD endpoints. In addition, summary of data for all FBF ratio endpoints will be provided including geometric means (and corresponding 95% confidence interval) and between-subject coefficients of variation (CVb) will be calculated by treatment group, where:

$CVb(\%) = \sqrt{\exp(SD^2) - 1} \times 100$ where SD is the standard deviation of the log_e-transformed data.

Mean (standard error [SE]) plots of the change from baseline FBF ratio data will be produced by treatment group. Separate plots will be produced for the FBF ratio for each challenge agent.

Further details will be included in the RAP.

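### Do the missing geometric means, CVb and confidence intervals, and a mislabelled column in shell PD_T2, undermine the reporting of the primary FBF ratio endpoint?

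*SAP*

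**What the plan says.** Protocol 10.3.3 sets two layers of description. For all pharmacodynamic endpoints: "Descriptive statistics (n, arithmetic mean and corresponding 95% confidence interval, standard deviation (SD), minimum, median, maximum) will be calculated by treatment group". For the FBF ratio it adds a second layer: a "summary of data for all FBF ratio endpoints will be provided including geometric means", these with 95% intervals, and it states that "between-subject coefficients of variation (CVb) will be calculated by treatment group", using the SD of the log-transformed data. The protocol's primary model also works on logs and back-transforms to a daprodustat/darbepoetin ratio.

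The SAP was written after termination. Its Table 1 (section 2.1) says of Protocol 10.3.3: "No statistical analyses will be performed; only summary statistics will be reported". The reason given is: "Since the study was terminated and we have only 4 completed subjects to report". Exploratory and sensitivity analyses are named as dropped. SAP 8.1.2 then gives the reduced list: "Descriptive statistics (n, arithmetic mean, standard deviation (SD), minimum, median, maximum) will be calculated by treatment group for change in FBF ratio endpoints". Shells PD_T1 and PD_T2 (SAP 10.11) show the same rows.

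In PD_T2, which serves Tables 3.2, 3.4 and 3.6, the two treatment columns carry footnote 1. That footnote forms each participant's Day 42 FBF ratio divided by the Day 1 ratio. The third column is headed, up to its footnote mark, "Change in FBF Ratio [2", and the matching footnote reads "2] The FBF ratio difference between Daprodustat and rhEPO".

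**The concern.** The two documents differ on how the primary endpoint is summarised. The sample size and the planned model are on the log scale, where the geometric mean and CVb are the natural summaries. The SAP keeps only natural-scale statistics plus the median. The protocol presents the omitted items as descriptive statistics and data summaries, so a literal reading of Table 1 retains them while 8.1.2 leaves them out. That looks like an undeclared departure on the primary endpoint.

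The PD_T2 column looks worse. A reader could take a between-arm contrast for a within-participant change. The arms are parallel, so a between-arm difference has no participant-level SD, minimum, median or maximum. If the difference is a subtraction, it also leaves the protocol's ratio scale. At stake would be a primary-endpoint table that is misread, or that reports something other than the planned quantity.

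**Working it through.** **Inputs.** CV 0.277 (Protocol 10.1); SD 0.272 and a true effect of 25% (Protocol 10.3.4); 4 completers (SAP Table 1); no per-protocol exclusions (SAP 10.1.1). The split by arm is not given. I assume 3/1 or 2/2. The numbers printed in the shells are placeholders: in PD_T1 the mean of 1.75 exceeds the maximum of 1.4.

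**1. The plan's own figure.** Log SD = sqrt(ln(1 + 0.277²)) = 0.272, which matches Protocol 10.3.4. So the design is on the log scale.

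**2. Distance between arithmetic and geometric mean.** With no true change, the expected arithmetic mean of Day 42/Day 1 is exp(0.272²/2) = 1.038, against a geometric centre of 1.00. The SD of the ratio is sqrt((exp(0.272²) − 1) × exp(0.272²)) = 0.288.
- n = 3: SE = 0.288/√3 = 0.166, and 0.0377/0.166 = 0.23 of an SE.
- n = 2: SE = 0.288/√2 = 0.203, and 0.0377/0.203 = 0.19 of an SE.

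**3. What the retained statistics already show.** With three participants in an arm, the minimum, median and maximum are the three values. With two, the minimum and maximum are both values. With one, they coincide. Example at −1, 0 and +1 planning SD: 0.762, 1.000 and 1.313.
- Arithmetic mean = 3.075/3 = 1.025.
- Geometric mean = (0.762 × 1.000 × 1.313)^(1/3) = 1.000. The SAP's median is also 1.000.
- Log values −0.272, 0, +0.272 have SD 0.272, so CVb = sqrt(exp(0.272²) − 1) = 0.277.

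All of this follows from the table, up to rounding. Listing 17 also gives each participant's FBF ratio by challenge dose.

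**4. What the omitted intervals would look like**, around a geometric mean of 1.00:
- n = 3: exp(±4.303 × 0.272/√3) = 0.51 to 1.97.
- n = 2: exp(±12.706 × 0.272/√2) = 0.09 to 11.5.
- n = 1: not computable, and neither is CVb.

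**5. The PD_T2 column.** The heading conflicts with the footnote, but the footnote says what the column is. In the extracted shell no values stand in that column, so the text does not show that an SD or range was intended for it. On scale, if the arms were subtracted, a true ratio of 1.25 would have expected value 0.25 × d × 1.0377, where d is darbepoetin's own Day 42/Day 1 ratio. That gives 0.18, 0.21 and 0.26 for d = 0.7, 0.8 and 1.0 (an assumed range), whereas a ratio of geometric means targets 1.25 throughout. But the word "difference" does not establish subtraction: Protocol 10.3.3 uses it for a treatment contrast that it then back-transforms to a ratio.

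**6. Precision of any between-arm figure.** The log-scale SE is 0.272 × sqrt(1/3 + 1) = 0.314 for 3/1, or 0.272 × sqrt(1/2 + 1/2) = 0.272 for 2/2. Even with the SD treated as known, the 95% margin is 1.96 × 0.314 = 0.615 or 1.96 × 0.272 = 0.533. The planned effect is ln 1.25 = 0.223.

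**The case for a change.** The strongest argument for acting is that the record is incomplete. The protocol itself files the intervals, geometric means and CVb under description, so Table 1's statement that summary statistics remain does not by itself remove them. Table 1 also records much smaller changes, such as a section reference added to the per-protocol population definition, so one more entry would have fitted. SAP 2.4 states the null hypothesis as a difference of zero, which lends some support to reading the PD_T2 footnote as a subtraction. A programmer has to decide what goes in that column.

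The factual part stands: the statistics are not named as dropped, and the heading and footnote disagree. The consequence does not follow. Table 1 identifies the protocol section, reduces it and gives the reason, and 8.1.2 then states exactly what will be reported. The protocol leaves further detail to this plan. Confidence intervals can fairly be read as part of the inference that was given up. Restoring the statistics would add figures that a reader can already derive, with intervals too wide to inform. Moving footnote 1's formula into 8.1.2 would only relocate text the SAP already contains. An unadjusted ratio of geometric means is planned in neither document and could rest on a single participant in one arm.

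**Conclusion.** The discrepancies are real but clerical, and no change to the plan follows. The omission is a reduction whose scope and reason are recorded in general terms, though not item by item. It costs about 3.8% between two measures of centre, roughly 0.2 of a standard error. It hides nothing, because every participant's value is visible in the tables or in Listing 17. The PD_T2 heading is a labelling slip that its footnote resolves, and an analyst can fill the column with a single descriptive contrast and label it as such. No test, decision or conclusion depends on either point.

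This rests on 4 completers, an arm split of 3/1 or 2/2, and the planning SD of 0.272. The subtraction figures also rest on an assumed darbepoetin ratio of 0.7 to 1.0 and on a reading of the footnote that the documents do not settle. Had the trial run to its planned 50 evaluable participants, the tabulated statistics would no longer reveal the individual values, and the same omission would deserve correction.
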